10.6 MEASURES TO MINIMIZE BIAS

10.6.1 ENROLLMENT/ RANDOMIZATION/ MASKING PROCEDURES

The device will be programmed to generate a different randomized active/silent schedule for each subject. Both the subjects and the investigators conducting statistical analyses will be masked as to when the device is in active/silent mode.

Data logged by the device during each mode will be coded either as mode A or B. The computer-generated coding for the active/silent modes for each subject will be saved as a computer file and stored in a secure location by a research team member who is not involved in data analyses.

Subjects will be masked in that they will not be informed when the device is in the silent or active mode. They will be told that the device may sometimes go into silent mode and not give any warning messages. They will be advised that they will not know when it is in silent mode and that they should be always vigilant about collision hazards.

The code for silent/active mode will not be broken until after the final data analyses are completed.

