Operation of the device will be straightforward. The controls will be designed to be easy for visually impaired or blind people to use. The device will be turned on by sliding the power switch to the on position and turned off by sliding it back to the off position. A plug-in charger will be provided for charging the battery. After the battery is fully charged, the device will run continuously for at least 6 hours. However, the actual period for which the device will operate will be longer than 6 hours as the device will switch to low power mode to save the battery when no walking of the participant is detected by the motion sensors within one minute. Once movement is detected, the device will turn on automatically. Depending on a person's activity level, the device may be able to function for several days without being charged. Wristbands will need to be charged separately from the device using their own charger. The wristband units hold the charge for about 5-6 days.

Generic backpack (≈ 1.8 lbs)

[figure not shown]

Figure 1. The entire collision warning device is contained in a backpack. It consists of two main parts connected by a wire. The main processing board (computing and data recording unit) is in the backpack. The camera is worn at chest level. The camera module also includes miniaturized motion sensors. The device can issue coded collision warnings via two Bluetooth vibro-tactile wristbands (one for each hand).

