10.4.2 ANALYSIS OF THE PRIMARY EFFICACY ENDPOINT(S)

The analysis will start with descriptive and graphical summaries of the rate of collision incidents (all contacts) in the active and silent modes, and the difference between active and silent modes. The rate will be computed as the rate of contacts per 100 true hazards (reviewed) per hour. The rate computation takes account of both duration of use and number of true hazards encountered, since some subjects might walk for longer but encounter fewer hazards while others might encounter more hazards in a shorter duration. Contacts will include all contacts with the collision hazard, either with their mobility aids (such as long cane) or body (touching with hand, bumping into the obstacle).

The primary analysis will start by comparing the within-subject difference in the rate of collisions (all contacts) between the active and silent modes using a Wilcoxon Signed-Rank test.

Next a model will be constructed to evaluate within-subject differences in the rates of collisions taking account of other factors that might affect the primary outcome measure. Since the number of contacts will represent overinflated count data, negative binomial regression models – considered to be more appropriate than Poisson regression models for such distributions – will be used for evaluating the association between rate of contacts and device operating condition (active vs. silent). In actual implementation of the regression model, the outcome will be set as the number of contacts (all contacts), while the exposure variable consisting of the duration of device use and the number of true hazards will be the offsets, and the estimated regression coefficients will be expressed as the rate ratio (β). The role of other possible predictors that could potentially affect the rate of contacts will be analyzed. These predictors will be taken from four broad categories: device data, demographics, vision characteristics, and mobility characteristics. Each predictor will be evaluated individually in a generalized mixed effects modeling framework (because we want to estimate within-subject effects) that will also include device condition. Any significant predictors ($p < 0.05$) and possible confounders (causing $\geq 10\%$ change in the rate ratio for the device condition predictor) will be selected for inclusion in the final model to determine the effect of device condition on rate of contacts.

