10.4.5 ADHERENCE AND RETENTION ANALYSES

The amount that the collision warning device is used each day will be recorded by the device and will be summarized with descriptive statistics. The number of participants who withdraw from the study after visit 1, after visit 2, and after starting to use the device at home will be recorded and summarized with descriptive statistics.

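### The primary rate divides contacts by hazards and again by hours, so a difference in hours between the two modes shifts the active/silent comparison by itself

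*Combined protocol and SAP*

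**What the plan says.** Section 10.4.2 defines the primary outcome rate: "The rate will be computed as the rate of contacts per 100 true hazards (reviewed) per hour". The reason given for using both denominators concerns differences between people: "some subjects might walk for longer but encounter fewer hazards while others might encounter more hazards in a shorter duration". The test, however, is within a person: "comparing the within-subject difference in the rate of collisions (all contacts) between the active and silent modes using a Wilcoxon Signed-Rank test". The regression that follows uses the same pair of denominators: "the exposure variable consisting of the duration of device use and the number of true hazards will be the offsets". Section 10.4.3 carries the method over to body contacts.

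On how time is shared between modes, section 10.6.1 says "The device will be programmed to generate a different randomized active/silent schedule for each subject". It gives no active:silent ratio, no block length and no balancing of walking time. Participants are told that "the device may sometimes go into silent mode and not give any warning messages", which does not imply a 1:1 split. Under section 6.1.11 the participant controls the power switch; the device is "turned off by sliding it back to the off position".

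On checking use, section 10.4.5 says "The amount that the collision warning device is used each day will be recorded by the device and will be summarized with descriptive statistics", with no breakdown by mode. Section 10.6.2 plans no evaluation of masking, and section 10.1 says there will be no formal SAP in which these details could be settled later.

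**The concern.** A rate is meant to absorb unequal exposure. Contacts per hazard does that, and so does contacts per hour. Dividing by both does not, because hazards met in a mode are themselves roughly proportional to the hours walked in it. After the first division time has cancelled; the second puts it back, upside down. The mode with more hours gets the lower rate whether or not the warnings work.

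Both planned primary analyses inherit this, as does the body-contact analysis. The stated justification, that people differ in how long they walk and how many hazards they meet, does not cover it, because the contrast of interest lies between two modes of the same person. The plan would therefore measure a mixture of the device effect and the split of hours, and it neither fixes that split nor plans to report it.

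**Working it through.** **1. The plan's own sample size.** Inputs from section 10.5: paired difference 0.2, SD of change 0.38, alpha 0.05 (two-sided, from the alternative hypothesis in section 10.2), power 0.80. A paired t-test with the noncentral t distribution gives n = 31 (power 0.809), as stated. That n is used in step 5; nothing else here depends on it.

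**2. Algebra of the rate.** For one participant in mode m, let T_m be hours, h hazards per hour (the same in both modes), H_m = h × T_m hazards, and p_m the contact probability per hazard, so expected contacts are C_m = p_m × H_m. Then

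planned rate = 100 × C_m / (H_m × T_m) = 100 × p_m / T_m.

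With r = p_active / p_silent (the true per-hazard ratio) and f the active share of hours,

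active rate / silent rate = r × T_silent / T_active = r × (1 − f) / f.

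The factor (1 − f)/f needs no assumed value for h or the contact risk.

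Example with no device effect (assumed 10 hazards/h, 10% contact risk): 12 h active gives 120 hazards and 12 contacts; 8 h silent gives 80 hazards and 8 contacts. Both modes have 10 contacts per 100 hazards. The planned rates are 10/12 = 0.83 and 10/8 = 1.25, a false 33% reduction.

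**3. Size over a range of shares.**

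| Active share f | Apparent ratio, no effect (r = 1) | Apparent ratio, true 20% reduction (r = 0.8) |
|---|---|---|
| 0.40 | 1.50 | 1.20 |
| 0.45 | 1.22 | 0.98 |
| 0.50 | 1.00 | 0.80 |
| 0.55 | 0.82 | 0.65 |
| 0.60 | 0.67 | 0.53 |
| 2/3 | 0.50 | 0.40 |

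A true effect vanishes when r(1 − f)/f = 1, that is at f = r/(1 + r): 0.8/1.8 = 0.444 for a 20% reduction and 0.7/1.7 = 0.412 for a 30% reduction.

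**4. The model.** With both offsets, log E(C) = log H + log T + (participant effect) + β × active. If contacts in truth follow p × H, the model can fit only with exp(β) = r × T_silent / T_active, which is the same factor.

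**5. Simulation of the planned Wilcoxon test, n = 31.** The documents give no use, hazard or contact rates, so these are assumptions: mean 30 h of use (lognormal), 4 hazards/h (gamma, CV 0.5), contact risk beta(2,8) with mean 0.2, and an active share with a 5-point SD between people.

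| Mean active share, no device effect | False-positive rate, planned rate |
|---|---|
| 50% | 0.05 |
| 52.5% | 0.15 |
| 55% | 0.48 |
| 60% | 0.94 |

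The same data analysed as contacts per hazard, or with common hours for both modes, stay near 0.05 throughout (about 0.04 to 0.06).

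For a true 20% reduction, power of the planned rate is about 0.63 at an exact 1:1 split, 0.52 when shares scatter around 1:1 with a 5-point SD, and about 0.06 at a mean share of 45%. Contacts per hazard keeps about 0.70 in all three.

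**6. Other inputs.** With a median of 20 h, 15 hazards/h and 15% contact risk, overdispersed contacts and a 10-point SD of share, the false-positive rate is about 0.20 at 55% and 0.60 at 60%. Symmetric scatter leaves it at 0.04 to 0.06, while power for a true 30% reduction falls from 0.58 (exact 1:1) to 0.46. The size moves with the inputs; the direction and the mechanism do not.

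**The case against.** - **Randomization should even out the hours.** If the schedule is 1:1 and use does not depend on mode, it does so on average, and type I error then stays near 0.05. This stands, and it limits the claim. Scatter between people still costs power.
- **A reader might infer that the schedule is tilted, or that participants will switch off in one mode, so that the trial's false-positive rate is lost.** The documents do not support that. Silence about the ratio is a gap in specification, not evidence of imbalance. Participants are told they will not know when the device is silent, warnings are limited to high-risk collisions, and no block length is given from which to judge whether a mode could be recognised. If vibration did lead people to switch off, active hours would fall and a benefit would be hidden rather than invented.
- **A reader might infer that use by mode cannot be checked.** It can: section 10.6.1 has data logged under a mode code, and a rate by mode needs hours and hazards by mode. Section 10.4.2 also lists device data among candidate predictors. What is missing is a commitment to report or compare hours by mode.
- **A reader might infer that unequal hours are the defect.** They are not; with a single denominator they would do no harm. The cause lies in section 10.4.2, and the silence of section 10.6.1 only leaves it unguarded.
- **Duration might mean a participant's total hours.** Hours would then cancel in the within-person ratio. The text does not say so, and a rate computed in each mode is more naturally read with that mode's hours.

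**Conclusion.** The point holds as a flaw in the definition of the primary rate. On the natural per-mode reading, the active/silent comparison is multiplied by silent hours / active hours in both the Wilcoxon analysis and the negative binomial model. This rests on hazards accruing with hours at the same pace in both modes; the shift does not depend on the other assumed rates.

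Whether the trial's conclusion would be biased depends on the average split of hours, which the documents leave open. An average tilt to 55% active gives a false 18% reduction, with simulated false-positive rates from 0.20 to 0.48 across the two sets of assumptions. A tilt the other way, to 45%, leaves 2.2% of a true 20% reduction (1 − 0.8 × 0.55/0.45). With no average tilt the harm is lost power only, about 0.63 to 0.52 in the scenario shown. Those power figures come from assumed inputs and are not a restatement of the plan's 0.80.

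**What to change.** - **Section 10.4.2 (the essential change):** use one exposure denominator for the within-person comparison and as the model offset, namely contacts per 100 true hazards. If hours are to stay, divide both modes of a participant by that participant's total hours, so that hours cancel within the person. Keep the planned double-denominator rate as a supportive analysis. Apply the same change to body contacts in section 10.4.3.
- **Section 10.6.1:** state the intended active:silent ratio.
- **Section 10.4.5:** report hours and true hazards by mode, under the A/B code until the code is broken, so that masking is kept.

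Running the schedule on accumulated walking time in balanced blocks is optional. It would recover balance, but it needs reprogramming, and regular blocks could make mode changes easier to guess.

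Cost: a few sentences in section 10, with no extra visits, data or participants. The downside is that the primary rate is redefined and no longer reflects hours in each mode, so the change should be made and documented before the code is broken.

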10.6.2 EVALUATION OF SUCCESS OF BLINDING

We have no plans to evaluate the success of masking.

10.6.3 BREAKING THE STUDY BLIND/PARTICIPANT CODE

The code for silent/active mode will not be broken until after the final data analyses are completed.

11 SOURCE DOCUMENTS AND ACCESS TO SOURCE DATA/DOCUMENTS

The PIs and study team will maintain appropriate research records for this clinical trial, in compliance with ICH E6 and regulatory and institutional requirements for the protection of confidentiality of participants. These records will include hard-copy record forms and electronic data from the collision warning device.

Schepens will provide direct access to source data/documents and reports for the purpose of monitoring and auditing by the sponsor, and inspection by local and regulatory authorities.

12 QUALITY ASSURANCE AND QUALITY CONTROL

QC procedures will be implemented beginning with all the data entered on hard copy record sheets and then entered into the electronic study spreadsheet (database). The records and data entries will be monitored on an ongoing basis by a second researcher, not responsible for original data entry. In prior studies we have found this to be a very effective method of ensuring data quality.

The PIs will be responsible for addressing quality assurance issues (such as correcting procedures that are not in compliance with the protocol) while the study coordinator will be responsible for correcting data entry errors.

Schepens will provide direct access to source data/documents, and reports for the purpose of monitoring and auditing by the sponsor, and inspection by local and regulatory authorities.

13 ETHICS/PROTECTION OF HUMAN SUBJECTS

13.1 ETHICAL STANDARD

The investigator will ensure that this study is conducted in full conformity with Regulations for the Protection of Human Subjects of Research codified in 45 CFR Part 46, 21 CFR Part 50, 21 CFR Part 56, and/or the ICH E6.

13.2 INSTITUTIONAL REVIEW BOARD

The protocol, informed consent form, recruitment materials, and all participant materials will be submitted to the IRB for review and approval. Approval of both the protocol and the consent form will be obtained before any participant is enrolled. Any amendment to the protocol will require review and approval by the IRB before the changes are implemented to the study. All changes to the consent form will be IRB approved; a determination will be made regarding whether previously consented participants need to be re-consented.

13.3 INFORMED CONSENT PROCESS

13.3.1 CONSENT/ASSENT AND OTHER INFORMATIONAL DOCUMENTS PROVIDED TO PARTICIPANTS

A consent form describing in detail the device, study procedures, and risks will be provided to each participant. Written documentation of informed consent will be required prior to starting the study. The consent form is included with this protocol. There is only one consent form which covers screening procedures and all other study procedures.

13.3.2 CONSENT PROCEDURES AND DOCUMENTATION

Informed consent is a process that will be initiated prior to the individual's agreeing to participate in the study and will continue throughout the individual's study participation. Extensive discussion of risks and possible benefits of participation will be provided to the participants and their families. The consent form will be IRB-approved and the participant will be asked to read and review the document. The investigator will explain the research study to the participant and answer any questions that may arise. All participants will receive a verbal explanation in terms suited to their comprehension of the purposes, procedures, and potential risks of the study and of their rights as research participants. Participants will have an opportunity to carefully review the written consent form and ask questions prior to signing. The participants will have an opportunity to discuss the study with their surrogates or think about it prior to agreeing to participate.

Participants in this clinical trial will be visually impaired or blind and may either have varying levels of difficulty in seeing the print on the hard copy consent form or may be totally unable to see the print. The following measures will therefore be implemented to ensure that all participants are able to independently access and review the information in the consent form. Participants will be allowed to use any assistive device they normally use to access printed documents such as optical magnifiers or video magnifiers. An electronic copy (pdf) of the consent form will be available for participants who prefer to view the document using magnification on their computer screen, or text-to-speech output. Braille copies of the consent form will be available for participants who prefer to read using Braille.

Each participant will sign the hard-copy informed consent document prior to any procedures being done specifically for the study. The participants may withdraw consent at any time throughout the course of the trial. A copy of the informed consent document will be given to the participants for their records. The rights and welfare of the participants will be protected by emphasizing to them that the quality of their medical care or other rehabilitation care will not be adversely affected if they decline to participate in this study.

13.4 PARTICIPANT AND DATA CONFIDENTIALITY

Participant confidentiality will be strictly held in trust by the participating investigators, their staff, and the sponsor. Therefore, the study protocol, documentation, data, and all other information generated will be held in strict confidence. No information concerning the study or the data will be released to any unauthorized third party without prior written approval of the sponsor.

Only research personnel involved in the project that have completed Protection of Human Subjects training will have access to study records and data. Authorized representatives of the sponsor, or representatives of the IRB may inspect all documents and records required to be maintained by the investigator, including but not limited to data forms for the participants in this study. The study site will permit access to such records.

The study participant's contact information will be securely stored for internal use during the study. At the end of the study, all records will continue to be kept in a secure location for as long a period as dictated by local IRB and Institutional regulations.

Procedures to minimize risks to confidentiality include recording demographic and contact information on a separate form from the rest of the experimental data, storing in locked file cabinets all forms or records with information about a subject that would allow identification, and the use of unique subject identifier codes on all experimental research data forms and electronic data files. The unique identifier codes will be known only to the members of the research group, and will be recorded in a file retained in a locked cabinet. Any electronic data files that would allow subject identification are password protected and on a secure server. All hard copy forms containing individually identifiable private information that is no longer required is shredded. Before the video clips of collision incidents recorded by the collision warning device are reviewed, an algorithm will be applied to automatically detect faces in the pictures and to cover each face with a blurring mask so that they are unrecognizable to assure anonymity. The face of a participant will never be in any of the pictures because he/she will be wearing the device.

All data will be stored and analysed at Schepens Eye Research Institute.

13.4.1 RESEARCH USE OF STORED HUMAN SAMPLES, SPECIMENS OR DATA

N/A

13.5 FUTURE USE OF STORED SPECIMENS

N/A

14 DATA HANDLING AND RECORD KEEPING

14.1 DATA COLLECTION AND MANAGEMENT RESPONSIBILITIES

All data will be obtained by non-invasive methods and will include data captured on paper records and electronic data recorded by the collision warning device. Data that will be captured on paper records will include vision measures (e.g., visual acuity, visual fields), demographic details, results from cognitive tests (e.g., Short Portable Mental Status Questionnaire, and the Bells test and Schenkenberg line bisection test for visual spatial neglect), responses to questionnaires (the Independent Mobility Questionnaire and the device questionnaire), and data on adverse events. Data entered on the paper

records at each study visit will be transferred to a customized electronic study spreadsheet (database) in a timely manner (within one week of the study visit).

The electronic study spreadsheet and electronic data from the collision warning device will be stored on a secure password protected server and on password-protected desktop computers of research personnel involved in the project. Hard copy record sheets that do not contain personally-identifiable information will be stored in study binders in locked offices (these record sheets use subject identifier codes). Hard copy record sheets that contain personally-identifiable information (such as consent forms and referral letters) will be stored in a locked file cabinet in a locked office. All hard copy forms containing individually identifiable private information that is no longer required will be shredded.

Data collection will be the responsibility of the clinical trial staff at Schepens under the supervision of the PIs. The investigator is responsible for ensuring the accuracy, completeness, legibility, and timeliness of the data reported. Data integrity and quality will be monitored on an ongoing basis by a second researcher, not responsible for original data entry. All source documents will be completed in a neat, legible manner to ensure accurate interpretation of data.

